6.4. Treatment withdrawal criteria

Patients **MUST** be withdrawn from the study **treatment** if any of the following occur:

- Pregnancy
- Serious adverse event (SAE) related to the study treatment
- Serious infection requiring IV antibiotics
- Development of blood dyscrasia, malignancy or demyelinating disorder
- Major surgical intervention
- Withdrawal of consent
- Chief or Principal Investigator decision
- Sponsor decision
- Poor patient compliance with study protocol (< 80% attendance of study visits)
- Poor patient compliance with study treatments (basic assessment/history in clinic/diary cards for Benepali)
- Omission of treatment > 4 weeks
- Transaminase raise > 3 x ULN
- Serum creatinine >175 µmol/L /eGFR below 30ml/L/min/1.73m²

Patients withdrawn from treatment will continue to be followed using the eCRFs for the duration of the study.

Patients will be **FULLY** withdrawn from the study only if they request so. Please, see section 6.5.5.

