9.4.6. Unscheduled visits

- For patients who do not tolerate their medication or are flaring outside of the study schedule.
- Will be recorded in the medical notes and in the CRF.
- If side effects related to IMP to be recorded as an adverse event
- Any changes to treatment to be documented

- **General**

- Assess compliance with treatment
- Clinical observations will be performed as per standard care (not required as a research parameter)
- Medication, allergy and co-morbidity check

- **Clinical assessment data**

- Physical examination if clinically indicated

- **Laboratory tests**

- Routine haematology and biochemistry suitable for diagnostic investigation & therapeutic DMARD monitoring FBC, U&E, LFT & eGFR ml/min/1.73 m²
- Urinalysis/pregnancy test if clinically indicated

- **Adverse event recording**

If the reason for the visit is a flare, the following assessments will also be done:

- **Clinical assessment data**

- Joint examination performed by an independent assessor:
 - Tender joint count (28)
 - Swollen joint count (28)
- Disease activity score (DAS28)
- Clinical disease activity index (CDAI)
- Simplified disease activity index (SDAI)
- Early morning stiffness (mins)

- **Laboratory tests**

- *Naïve CD4+ T-cells*
- ESR (mm/h) & CRP (mg/L)

- **Patient reported outcomes**

- Visual analogue scores of pain/disease activity/general health
- Physician assessment of general health
- HAQ-DI

- ***Imaging***

- o Power Doppler Ultrasound (PDUS) of standard set of 26 and 6 tendons joints for grey-scale (GS), power Doppler (PD), erosions (E) and osteophytes (O) and tenosynovitis (TSV)
- Management of DMARD treatment/administration of corticosteroid treatment will be at the discretion of the treating study physician

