### 11.2.2 Analysis visit windows

Visit windows will be used for all assessments unless specified otherwise. The actual day of an assessment will be mapped to the planned study visit using the following rules:

- If more than one assessment falls within a visit window, the closest non-missing assessment to the scheduled day will be used in the analysis.
- If more than one non-missing assessment actual dates are equidistant from the target day, the earlier assessment will be used in the analysis.

The windows for the analysis visits, split by the mid-point between the visits, are given in Table 3.

*Table 3: Analysis visit windows*

Timepoint	Study day	Analysis visit window in days
Week 0 (baseline)	1	All assessments prior to first dose of IMP
Week 4	29	Assessments post first dose of IMP to Day 57
Week 12	85	58 to 127
Week 24	169	$\geq 128$

The study day will be calculated as:

$$\text{Study day} = \text{Actual visit or assessment date} - \text{date of initial IMP dose} + 1$$

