### 11.7.2 Laboratory measurements

Laboratory parameters from haematology (full blood count) and biochemistry tests (eGFR, LFT, urea and electrolytes) will be summarised descriptively by visit for each trial group and overall.

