## 16 Appendices

### Appendix 1: Primary outcome table shells

*Descriptive statistics of DAS28(ESR) and clinical remission by visit*

	Group A (N=XX)				Group B (N=XX)				Group C (N=XX)			
	Baseline	4 weeks	12 weeks	24 weeks	Baseline	4 weeks	12 weeks	24 weeks	Baseline	4 weeks	12 weeks	24 weeks
Disease Activity Score-28 (DAS-28 (ESR))												
n												
Mean (SD)												
Median (IQR)												
Min-Max												
Missing												
Clinical Remission												
Clinical remission achieved (DAS28 ≤2.6) N (%)												
Clinical remission not achieved (DAS28 ≤2.6) N(%)												
Missing												
Sustained clinical remission achieved N(%)												

Similar descriptive statistics tables will be produced for PROMs, imaging remission, T-cell status, SDAI and CDAI and laboratory measurements.

*Difference in proportions achieving clinical remission by visit, Full analysis set*

[figure not shown]
	n	Proportion	Adjusted difference in proportions (95% CI)	Unadjusted odds ratio (95% CI)	Adjusted odds ratio (95% CI)	p-value
Week 4						
Arm A						
Arm B						
Week 12						
Arm A						
Arm B						
Week 24						
Arm A						
Arm B						

Trial Arms are defined as: **Group A** -T2T care with methotrexate (normal T-cell frequency), **Group B**-T2T care with methotrexate (abnormal T-cell frequency)

Comparisons are relative to Arm B

Patients who discontinue study treatment early are considered as non-responders

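### The SAP's one-value-per-window rule also governs safety bloods, so the by-visit laboratory tables can omit unscheduled abnormal results, and no planned output counts patients who cross the protocol 6.4 laboratory limits

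*SAP*

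**What the plan says.** SAP 11.2.2 sets the scope broadly: "Visit windows will be used for all assessments unless specified otherwise". Within a window one value is kept: "If more than one assessment falls within a visit window, the closest non-missing assessment to the scheduled day will be used in the analysis". Ties go to the earlier date: "If more than one non-missing assessment actual dates are equidistant from the target day, the earlier assessment will be used in the analysis". Table 3 gives target days 29, 85 and 169 for Weeks 4, 12 and 24. The windows are "split by the mid-point between the visits", with cuts at days 57 and 127, and the Week 24 window has no upper limit.

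SAP 11.7.2 says that full blood count, eGFR, liver function, and urea and electrolytes "will be summarised descriptively by visit for each trial group and overall". SAP Appendix 1 adds: "Similar descriptive statistics tables will be produced for PROMs, imaging remission, T-cell status, SDAI and CDAI and laboratory measurements". The shell referred to has columns for baseline and Weeks 4, 12 and 24 only.

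Protocol 9.4.6 describes unscheduled visits as being "For patients who do not tolerate their medication or are flaring outside of the study schedule", and lists FBC, U&E, LFT and eGFR among the tests. Protocol 6.4 lists laboratory findings that require withdrawal from study treatment: "Transaminase raise > 3 x ULN", serum creatinine above 175 µmol/L, and eGFR below 30.

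**The concern.** Choosing the value nearest the target day is sensible for efficacy, where each visit needs one representative score. It suits safety bloods less well, because what matters there is whether a patient ever had a bad value.

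The selection is also related to the outcome. A patient who does not tolerate treatment may attend between scheduled visits. An abnormal result then can lead to a change of treatment, after which the next scheduled result may be normal. The rule favours the scheduled result. The by-visit tables could then look unremarkable in an arm where some patients met a 6.4 laboratory limit.

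What is at stake is the laboratory description of methotrexate alone against methotrexate plus etanercept, in arms planned at 16 to 30 patients each. No primary or secondary efficacy result depends on it.

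**Working it through.** **1. Table 3 cut days.** The mid-points are (29 + 85)/2 = 57 and (85 + 169)/2 = 127. Both match the SAP.

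**2. When a result is lost.** Let t be the target day, s the day of the scheduled result and d the day of an unscheduled result in the same window. The unscheduled result is dropped if |d − t| > |s − t|, or if the two distances are equal and d is later than s. Otherwise it is kept.

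- Dropped: a transaminase above 3 × ULN on day 60 and a normal value at Week 12 on day 85. Both days lie in the window 58 to 127. The distances are 25 and 0, so only day 85 is tabulated.
- Kept: an unscheduled result on day 80 when Week 12 was attended on day 92. The distances are 5 and 7, so day 80 is tabulated.
- Kept: any unscheduled result that is the only one in its window, for example after a missed scheduled visit.

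**3. How much of the calendar is exposed.** Protocol 9.1 allows scheduled visits within ±7 days. The table counts the other days in each window on which one unscheduled result would be dropped, given one scheduled result in that window. Two assumptions are needed: the Week 4 window starts on day 2, and the Week 24 window closes in practice on day 176 (169 + 7).

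| Window | Scheduled visit on target | Scheduled visit 7 days off target |
|---|---|---|
| Week 4 (days 2–57) | 55 of 55 | 41–42 of 55 (75–76%) |
| Week 12 (days 58–127) | 69 of 69 | 55–56 of 69 (80–81%) |
| Week 24 (days 128–176) | 48 of 48 | 34–35 of 48 (71–73%) |

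For Week 12 with the visit 7 days off, days 58–77 (20 days) and 93–127 (35 days) are more than 7 days from target, so 20 + 35 = 55 days lose. The tie adds one more day when the scheduled visit was the early one. The other windows follow in the same way.

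These are shares of calendar days on which a result could fall. They are not shares of results or of patients.

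**4. Whether another planned output recovers the values.**

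- SAP 11.2 gives minimum and maximum, but 11.2.2 means that these are taken over the selected values.
- SAP 11.7.1 counts serious and non-serious adverse events by arm. It splits serious events by seriousness criterion, relationship and outcome, and non-serious events by relationship and outcome. Neither is split by event type or organ system.
- Protocol 12.6 gives line listings for serious events only.
- SAP 11.3 reports withdrawals with reasons where these are available. It does not say whether withdrawal from treatment alone, which protocol 6.4 separates from leaving the study, is included.
- Neither document plans a worst post-baseline value, a shift table, a count of threshold crossings or a listing of out-of-range results.

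**5. Two gaps that affect any repair.**

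- Study day in SAP 11.2.2 runs from the first IMP dose. Protocol 1.2 and 7.1 class only the etanercept biosimilar as IMP, so Arms A and B have no such date as written.
- Protocol 9.4.6 lists FBC and biochemistry for unscheduled visits generally. The schedule in 9.1 marks them with footnote a, which restricts them to flare visits. SAP 7.3 says that these parameters are collected at all visits.

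**The case against.** The strongest reply is that adverse event reporting already covers such cases. Protocol 10.1 allows an abnormal laboratory finding to be an adverse event, events are recorded at unscheduled visits too, and the counts in SAP 11.7.1 do not pass through the visit windows. Adverse events associated with stopping the IMP are a named safety variable. This stands in part. A reader might infer that these toxicities vanish from safety reporting, or that hepatic and renal risk cannot be compared between arms at all; the documents do not support that. What remains is that a non-serious liver enzyme rise recorded as an adverse event enters a total that no planned table identifies as hepatic.

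A reader might also infer that unscheduled toxicity results drop out as a rule, including every one that triggers withdrawal. They do not: loss needs a preferred value in the same window, and a trigger found at a scheduled visit will usually be kept.

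Nor does the calendar count measure loss. Days more than 7 from target number 41 + 55 + 34 = 130 of 56 + 70 + 49 = 175 (74%). It would be wrong to read this as three quarters of results lost, because tests are not spread evenly over days and the figure rests on the assumed close at day 176. Likewise, one missed case is 1/16 = 6.3 points in the smallest arm and 1/30 = 3.3 points in the largest planned Arm B or C, but the SAP does not estimate that incidence, so neither figure is an error in a planned result.

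Finally, protocol 12.6 promised only SAE summaries, so SAP 11.7.2 already goes further, and the comparison of Arms B and C is descriptive. This bears on priority. It does not alter how the rule works.

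**Conclusion.** The point holds as a limited weakness of the laboratory safety tables. On the text, an unscheduled FBC, LFT, U&E or eGFR result is omitted whenever a nearer value, or an equally near earlier one, lies in its window. Because an abnormal result can lead to action that normalises the next one, the omission can understate toxicity. No planned output gives the number of patients per arm who met a 6.4 laboratory limit.

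The size cannot be stated. The documents give no frequency for unscheduled tests or for laboratory toxicity. With a scheduled result in the window, the exposed share of days runs from about 71% (visit 7 days off target) to 100% (visit on target), but this describes only the reach of the rule. The conclusion assumes that 11.2.2 applies to laboratory data as written. Reading by visit in 11.7.2 to include unscheduled visits would need an exemption that is not there, and the table shell has no such column.

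**What to change.** In SAP 11.7.2:

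- State that the 11.2.2 selection rule does not apply to safety laboratory data in the added summary. Keep the by-visit tables.
- Using all post-first-dose results held in the CRF, scheduled and unscheduled, report by arm each patient's worst value and the number (%) meeting each laboratory limit in protocol 6.4: transaminase above 3 × ULN, creatinine above 175 µmol/L, eGFR below 30. The limits serve only as tabulation thresholds.
- Worst neutrophil, platelet and haemoglobin values can go in the same table. Counts against the protocol's limits for these are optional, since they are entry limits and not 6.4 withdrawal criteria.
- Define first dose for Arms A and B, where no IMP is given.

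Separately, reconcile footnote a of protocol 9.1 with 9.4.6 on whether FBC and biochemistry belong to all unscheduled visits or only to flare visits, so that the denominator of the new table is clear.

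The cost is a sentence or two in the SAP and one table, with no new data collection. One limit should be stated with the table: protocol 7.3.3 leaves routine DMARD blood monitoring to standard care and mentions CRF recording only for treatment changes, so between-visit results that never reached the CRF will not be included.

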### 11.2.3 Missing data

Individuals who discontinue study treatment will continue to be followed up, where possible, according to the study visit schedule. Patients who discontinue study treatment early due to lack of efficacy will be considered treatment non-responders from that point onward (not achieving clinical

or imaging remission). In the main analyses, patients with missing data for reasons other than lack of efficacy will also be considered non-responders. For patient-reported outcomes, the analysis will only include patients with data available.

Missing data for the baseline covariates which will be used in analyses (DAS28ESR, age, gender, smoking status) will be imputed with the mean or the modal value (for categorical variables). If there is a large amount of missing data for a covariate then it will be considered whether to remove the variable from analysis models.

For the analyses of the T-cell status, missing age will be imputed with the mean for the calculation of the threshold for normal T-cell status. If the T-cell frequency is missing then the status will be set to abnormal if the missing data is due to lack of efficacy, otherwise the status will be set to missing.

In cases where there are a lot of missing data in secondary outcomes, best and worst-case imputation may be considered as ad-hoc analyses to assess the impact of exclusion.

### **11.3 Screening, eligibility, recruitment and follow-up data**

The following information from the screening and eligibility processes will be reported in tabular format (by treatment arm and overall) and in the CONSORT flow diagram:

- The number of participants screened
- The number/proportion of eligible/ineligible participants
- Reasons for ineligibility
- The number of eligible participants approached for consent
- The number of participants that did/did not consent
- Reasons for non-consent

Frequency of and timing of withdrawals will be presented overall and by randomised group, with reasons where available. A template of the CONSORT diagram can be found in Appendix 2.

A recruitment graph will present the overall recruitment by month and this will also be available in tabular form. A graph of the actual vs target recruitment may also be produced where the target recruitment will be calculated based on the overall average recruitment rate per site per month.

The rate of missing data for each outcome at each follow up point will be presented by trial arm and overall, as stated in section 11.5.

### **11.4 Baseline data**

Baseline data for all randomised participants (except any ineligible patients randomised in error) and for only those included in the primary analysis, will be summarised descriptively by trial arm and overall. Parameters summarised will include demographics, vital signs, smoking status, alcohol intake and medical history. Continuous baseline data will be summarised in terms of the non-missing sample size, arithmetic mean, standard deviation, median, interquartile range, minimum and maximum. Categorical baseline data will be summarised in terms of frequencies and proportions. No formal between group comparisons of baseline data will be undertaken. Tables illustrating this are given in Appendix 3.

Unless otherwise specified, the last valid measurement before study medication administration will be utilised as the baseline value.

### **11.5 Analysis of primary outcome**

The primary outcome will be summarised descriptively by trial arm and overall at each time point, including the level of missing data.

### 11.5.1 Primary analysis

The estimand for the primary outcome is the difference in the proportion of patients in clinical remission (DAS28ESR  $\leq 2.6$ ) at 24 weeks of first-line methotrexate with T2T care between those with normal (Arm A) vs. abnormal (Arm B) naïve CD4+ T-cell frequencies, with patients who discontinue study treatment early due to lack of efficacy considered as treatment non-responders.

The primary endpoint will be analysed using binary logistic regression in the FAS. The model will adjust for DAS28ESR at baseline, age (at baseline), gender, smoking status (binary; current or previous vs never), and trial arm. Participants with missing data will be imputed as treatment non-responders.

The treatment effect will be presented in the form of both unadjusted and adjusted odds ratios, along with the corresponding two-sided 95% Wald CIs and p-values. Model coefficients for the covariates with 95% Wald CIs will additionally be presented to aid understanding of the fitted model. The model coefficients will be used to calculate the marginal proportions and difference in proportions. Two-sided bias-corrected 95% CIs will be calculated via non-parametric bootstrapping.

Model assumptions will be checked as follows: the multicollinearity between variables can be checked using the variance inflation factor (VIF), which measures the correlation and strength of correlation between the predictor variables in a regression model. Checks for influential observations and outliers will be conducted using Cook's Distance and if any are detected then sensitivity analyses will be completed to assess the impact on the model when these observations are removed. Graphs will be plotted of each explanatory variable against the logit of the response variable to assess if the relationship between them is linear. Transformations of the variables included in the model may be considered. If assumptions are not met, appropriate non-parametric tests will be considered.

If the model does not converge then smoking status will be removed from the model. If there are still issues with convergence, resulting in a sparse dataset and complete/ quasi-separation, then Firth logistic regression [4] may be used instead. This is similar to the logistic regression model but includes a penalisation term in the likelihood function.

Table templates for the primary outcome descriptive summaries and results are given in appendix 1.

The primary analysis will be checked by a second statistician on completion which will be documented using *F16: Primary Analysis Sign Off Form*.

#### 11.5.1.1 Sensitivity analyses

##### Per protocol

The primary analysis will be repeated in the set of patients treated according to protocol (PPS).

##### Missing data

Details concerning the extent and reasons for missing primary endpoint data will be reported by trial arm. The primary analysis assumes that all patients with missing data are non-responders. This assumption will be tested by conducting sensitivity analyses using the FAS, including best-case single imputation for these patients (which corresponds to imputing them as responders), complete case analysis and, in addition, multiple imputation may be considered.

For participants with missing data due to lack of efficacy this will remain imputed as treatment non-responders.

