6.5.4. Study blinding

- Patients will not be blinded to treatment. Patients will not be told their T-cell result however, those randomised to receive Benepali® will know they will have abnormal T-cell subsets as this will be outlined in the PIS.
- Clinicians will not be blinded to treatment or T-cell result, however the joint count will be conducted independently by a suitably qualified and competent individual (as an independent joint assessor [IJA]) to minimise bias. This individual will not be involved in patient care and will be instructed not to discuss disease activity or treatment with patients or Principal Investigator.
- Ultrasound scans will be performed by sonographers blind to treatment allocation and T-cell result; patients will be instructed not to discuss details of their treatment during their scan.
- Randomisation codes will remain blinded to clinicians recruiting to the study as these will be administered centrally.

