12.7. Handling of dropouts and missing data

Wherever possible, patients who discontinue study treatment will continue to be followed up according to the study visit schedule. Patients who discontinue study treatment early due to lack of efficacy will be considered non-responders from that point onward (not achieving clinical or imaging remission). In the main analysis, patients with missing data for reasons other than lack of efficacy will also be considered non-responders; sensitivity analyses will include best-case and worst-case single imputation for these patients, complete case analysis and, if possible, multiple imputation. For patient-reported outcomes, the primary analysis will only include patients with data available; sensitivity analyses will include best-case and worst-case single imputation for patients with missing data and, if possible, multiple imputation.

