# 7. Outcomes

## 7.1 Primary outcome

The primary outcome is the difference in the proportions of patients in clinical remission at 24 weeks of first-line methotrexate with T2T care between those with normal (Arm A) vs. abnormal (Arm B) naïve CD4+ T-cell frequencies at baseline.

The Disease Activity Score (DAS28ESR) is a combined index that measures disease activity in patients with Rheumatoid Arthritis (RA). It has been extensively validated for its use in clinical trials. It incorporates the tender 28-joint count (TJC28), the swollen 28-joint count (SJC28), erythrocyte sedimentation rate (ESR; mm/hour) and patient global/general health assessment VAS (mm).

The TJC28 and SJC28 are calculated from the assessment of the same 28 joints where each joint is determined to be either tender or not tender and either swollen or not swollen. The assessment will be performed by an independent assessor to minimize bias. Where possible, the same assessor should preferably perform the TJC and SJC for a given patient particularly during the study to minimize inter-observer variation.

Missing joint assessments will typically result in a missing count, however there are several cases of this (see CTT20 'multiple IJA missed entry') where they will be imputed as 0 due to confidence

expressed by the PI that the missing CRF fields should have indicated that the joint was not affected. In most of these cases only a few assessments were missing per participant.

The formula for DAS28(ESR) is:

$$DAS28(ESR) = 0.56\sqrt{TJC28} + 0.28\sqrt{SJC28} + 0.014(GH) + 0.70\ln(ESR)$$

The DAS28ESR will automatically be calculated within the MACRO system and computed at the analysis stage from the stored DAS28ESR components. Note that ESR values of 0 will be input as 0.001 to allow for them to be compatible with the DAS28 formula (i.e.  $\ln(0)$  is undefined). The DAS28ESR ranges from 0-10 with higher scores indicating greater disease activity. If any of the components are missing, then DAS28ESR will be missing. Clinical remission (primary endpoint) will be deemed to have been achieved if  $DAS28ESR \leq 2.6$ .

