### **Missing joint assessments**

Several deviations have occurred indicating missing joint assessments and in the main model these were assumed as 0. Since these will impact directly on the primary outcome (see section 7.1), a sensitivity analysis will be conducted on the main primary model replacing these assessments as missing. This will result in missing DAS-28 scores and as per section 11.2.3, they will be imputed as treatment non-responders.

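### The single imputations planned for missing remission data move both arms the same way, so their agreement does not bound the A–B difference; the only check on zero-filled joints has the same limit

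*SAP*

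**What the plan says.** **Missing outcomes.** In the SAP's Missing data paragraph (11.5.1.1), "The primary analysis assumes that all patients with missing data are non-responders". The same paragraph says this assumption will be tested in the full analysis set, "including best-case single imputation for these patients (which corresponds to imputing them as responders), complete case analysis", and "in addition, multiple imputation may be considered". One group is held fixed throughout: "For participants with missing data due to lack of efficacy this will remain imputed as treatment non-responders".

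Protocol 12.7 states that "sensitivity analyses will include best-case and worst-case single imputation for these patients", without saying whether best and worst are defined within each arm or for the comparison. The SAP defines best case as response for everyone and lists no worst case. On that definition the worst case is the main analysis itself.

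**Supplementary models (SAP 11.5.1.2).** The repeated-measures logistic model again codes missing as non-response. The mixed model for continuous DAS28ESR uses available data without imputation.

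**Missing joints.** SAP 7.1 lists several cases of blank joint fields "where they will be imputed as 0 due to confidence" on the part of the PI that the joints were unaffected. The sensitivity analysis sets those fields back to missing. DAS28 is then missing, and "they will be imputed as treatment non-responders". The SAP amendment log gives the number of participants affected as one reason for the change. Neither document gives a count, overall or by arm.

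**The concern.** The primary estimand (SAP 11.5.1) is a difference between two arms. Coding every missing patient as a failure and then every missing patient as a responder raises both arms together, and most of the effect cancels from the difference. The extremes of a difference lie at the opposite-direction corners: missing A fail with missing B respond, and the reverse. Neither document plans these, nor a tipping-point or delta-adjusted analysis.

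The stake is interpretive. If the required analyses agree, the report could call the result robust to missing data when significance still rests on a few unobserved patients, mainly in the small Arm B. The arms are defined by the biomarker and treatment is open-label, so similar missingness mechanisms in the two arms should not be taken for granted.

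The joint check raises the same issue. Filling with zero can only lower DAS28. The only alternative makes every affected patient in both arms a non-responder, including any whose remission status could not change whatever the missing joints showed.

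**Working it through.** **Planning figures (Protocol 12.9, SAP 9).** Remission 68% in A and 25% in B, ratio 2.75:1, two-sided 5%, 80% power, variance inflation 1.05, 10% drop-out. The pooled two-proportion formula gives 13.32 in B, and 13.32 × 3.75 = 49.94 in total. Then 49.94 × 1.05 = 52.43, rounded up to 53 as stated. Drop-out gives 53 / 0.9 = 58.9, so 59 against the stated 60. The arm sizes 44/16 (minimum) and 46/30 (maximum) are used below.

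**Assumed, not in the documents:** missing counts by arm, set near the planned 10%, and observed remission counts near the planned rates. Tests are unadjusted Wald tests on the log odds ratio.

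**Algebra.** Let r be observed remitters, m missing and n arm size.
- All non-responder: rA/nA − rB/nB.
- All responder: this changes by mA/nA − mB/nB.
- Full range between the opposite-direction corners: mA/nA + mB/nB.

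At 44/16 with 4 and 2 missing, 4/44 = 9.1% and 2/16 = 12.5%. The two planned imputations differ by 3.4 points; the full range is 21.6 points. At 46/30 with 5 and 3 missing the figures are 0.9 and 20.9 points.

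**Example at 44/16, with 27 of 40 and 4 of 14 observed remitters:**

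| Analysis | A | B | Difference (points) | OR (95% CI) | p |
|---|---|---|---|---|---|
| Main: all non-responder | 27/44 | 4/16 | 36.4 | 4.76 (1.32–17.21) | 0.017 |
| Best case: all responder | 31/44 | 6/16 | 33.0 | 3.97 (1.20–13.22) | 0.024 |
| Complete case | 27/40 | 4/14 | 38.9 | 5.19 (1.37–19.73) | 0.016 |
| Missing A fail, missing B respond | 27/44 | 6/16 | 23.9 | 2.65 (0.81–8.62) | 0.106 |
| Missing A respond, missing B fail | 31/44 | 4/16 | 45.5 | 7.15 (1.94–26.35) | 0.003 |

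For the fourth row, OR = (27 × 10)/(17 × 6) = 2.65, and the SE of the log OR = √(1/27 + 1/17 + 1/6 + 1/10) = 0.602.

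**A case that holds.** At 46/30 with 5 and 3 missing and 28/41 versus 7/27 observed, the adverse corner is 28/46 versus 10/30: 27.5 points, OR 3.11 (1.19–8.15), p = 0.021.

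**How often.** Exact binomial enumeration of the observed remitters at 68% and 25%, with missing counts fixed. At 44/16 with 4 and 2 missing, all three required analyses are significant in favour of A with probability 0.75. Among those outcomes the adverse corner loses significance in 38%. Other assumed counts give:
- 44/16: 14% (2 and 1 missing) and 51% (4 and 3 missing)
- 46/30: 26% (5 and 3 missing) and 80% (9 and 6 missing, about 20%)

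**Joints.** By the SAP 7.1 formula, one joint both tender and swollen, with all other joints at zero, adds 0.56 + 0.28 = 0.84. Two illustrative patients (general health and ESR values assumed) show the two situations:
- General health 20, ESR 20: 0.28 + 0.70 ln 20 = 2.38 with the joint unaffected and 3.22 with it affected. The fill decides remission.
- General health 10, ESR 5: 0.14 + 0.70 ln 5 = 1.27, or 2.11. This patient is in remission either way, yet the SAP check counts a failure.

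Now suppose 4 zero-filled patients in A and 2 in B all count as remitters in the main analysis. Main: 30/44 versus 6/16, p = 0.037. SAP check: 26/44 versus 4/16, p = 0.025. Changing only Arm A: 26/44 versus 6/16, OR 2.41 (0.74–7.81), p = 0.14. The planned check again agrees with the main result while an arm-specific change does not.

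**The case against.** Several points on the other side stand.

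- **Not every analysis imputes in one direction.** Complete case imputes nothing, multiple imputation has no fixed direction, and the continuous model uses available data. The criticism applies to the two single imputations. The others do not supply a bound.
- **The adverse corner is extreme.** If missing patients behaved like their arm, all four in A failing and both in B remitting has probability 0.32⁴ × 0.25² ≈ 0.0007. It serves as a bound and should not be offered as a likely pattern.
- **The example is the smallest design and unadjusted.** The SAP model also adjusts for baseline DAS28ESR, age, gender and smoking. In the main 44/16 enumeration significance is kept more often than lost.
- **There is mitigation.** The extent and reasons for missing primary data will be reported by arm, so a reader could work out the unadjusted corners. Patients who stop treatment continue to be followed. The SAP's list of checks is not worded as closed.
- **The joint fill has a rationale.** SAP 7.1 describes mostly a few blank fields per participant. The joint check moves only zero-filled patients otherwise in remission. With three missing joints, all others zero, up to 0.84 × √3 = 1.45 is added, so only a zero-filled score of at most 1.15 is certain remission. Where several joints are missing, bounding may leave many patients ambiguous.

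A reader might infer that the result could reverse. In the example A stays ahead by 24 points, so that does not follow. A reader might also note "Clinicians will not be blinded to treatment or T-cell result" (Protocol 6.5.4) and infer that knowledge of T-cell status shaped the zero-fill. The documents do not show that: the counts come from an independent joint assessor, and the decision is presented as correcting CRF completion. Nor does the absence of a worst case from the SAP lose information, since under its definition that would repeat the main analysis.

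**Conclusion.** The concern holds as a limit on what the planned checks can show. The SAP says the non-responder assumption will be tested, but its two single imputations span only mA/nA − mB/nB of a possible mA/nA + mB/nB: 3.4 of 21.6 points in the 44/16 example. Complete case can agree with both, and multiple imputation may not be done. Agreement among the required analyses is therefore not evidence that the A–B difference is robust to missing data. In that example significance is lost at the adverse bound; in the 46/30 example it is kept.

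The joint check likewise cannot separate patients whose classification depends on the fill from those whose classification is certain.

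The sizes rest on assumed missing counts, assumed zero-filled counts and unadjusted tests. The algebra does not depend on those assumptions. The main estimate and its non-responder rule are not in question.

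**What to change.** Add two sensitivity tables to SAP 11.5.1.1 before the arm codes are released to the statistician (the step in Protocol 12.10), leaving the primary analysis unchanged. If the codes have already been released, label the additions post hoc.

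1. **Tipping-point grid for missing outcomes not due to lack of efficacy.** Vary the number of missing patients counted as responders from 0 to mA in Arm A and from 0 to mB in Arm B. Include both opposite-direction corners and present them as bounds. With 4 and 2 missing the grid has 5 × 3 = 15 cells. Report the difference, odds ratio and interval in each. In the adjusted model, interior cells depend on which patients are chosen, so state the selection rule; the corners are unique.
2. **Bounded classification for zero-filled joints.** Compute DAS28 with the missing joints all unaffected and all affected. Fix the status where both scores fall on the same side of 2.6. Report by arm the numbers in certain remission, certain non-remission and ambiguous. Carry the ambiguous patients into the same arm-by-arm grid instead of setting them all to non-responder.

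Both tables use data already collected. The cost is two extra tables and possibly a less favourable bound than the current checks would show.
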